2.1 PROTOCOL SYNOPSIS

The protocol synopsis is in [Appendix 1](#). The schedule of assessments is provided in [Appendix 2](#). For additional details, see the study protocol.

2.2 ENDPOINTS

2.2.1 Primary Efficacy Endpoints

The primary efficacy endpoint is the investigator-assessed PFS per RECIST v1.1, defined as the time from randomization to the first occurrence of disease progression, as determined by an investigator according to RECIST v1.1, or death from any cause, whichever occurs first.

2.2.2 Secondary Efficacy Endpoints

The secondary efficacy endpoints are as follows:

- IRC-assessed PFS per RECIST v1.1, defined as the time from randomization to the first occurrence of disease progression, as determined by the IRC according to RECIST v1.1, or death from any cause, whichever occurs first
- Overall survival (OS), defined as the time from randomization to death from any cause
- Objective response, defined as a complete response or a partial response on two consecutive occasions ≥ 4 weeks apart, as determined by the investigator according to RECIST v1.1

- Duration of response (DOR), defined as the time from the first occurrence of a documented objective response to disease progression, as determined by the investigator according to RECIST v1.1, or death from any cause, whichever occurs first
- Time to deterioration in global health status, defined as the time from randomization to first observed \geq 10-point decrease in European Organization for Research and Treatment of Cancer Core Quality of Life Questionnaire (EORTC QLQ-C30) linearly transformed global health status scale score that is sustained for two consecutive assessments or followed by death while the patient is on treatment
- Time to deterioration in physical functioning, defined as the time from randomization to first observed \geq 10-point decrease in EORTC QLQ-C30 linearly transformed physical functioning scale score that is sustained for two consecutive assessments or followed by death while the patient is on treatment

2.2.3 Exploratory Efficacy Endpoints

The exploratory efficacy endpoints are as follows:

- [REDACTED]
- [REDACTED]
- [REDACTED]
- [REDACTED]
- [REDACTED]
- [REDACTED]

2.2.4 Pharmacokinetic Endpoints

The PK endpoints are as follows:

- Serum concentration of atezolizumab at specified timepoints
- Plasma concentration of cobimetinib and vemurafenib at specified timepoints

2.2.5 Safety Endpoints

The safety endpoints are as follows:

- Occurrence, frequency, and severity of AEs
- Change from baseline in targeted vital signs during and following treatment
- Change from baseline in targeted clinical laboratory test results during and following treatment

2.3 DETERMINATION OF SAMPLE SIZE

Approximately 500 patients will be randomized into the study.

The final analysis of the primary endpoint of PFS will take place when approximately [REDACTED] PFS events have occurred. Statistical considerations are based on the following assumptions:

- Stratified log-rank test at 0.05 significance level (two sided)
- [REDACTED]
- [REDACTED]
- [REDACTED]
- [REDACTED]
- [REDACTED]
- [REDACTED]

A total of [REDACTED] PFS events provides approximately [REDACTED] % power to detect an improvement in median PFS from [REDACTED]

2.4 ANALYSIS TIMING

The primary analysis will be conducted when approximately [REDACTED] PFS events have occurred, which is expected to occur approximately [REDACTED] months after first-patient-in (FPI). There is no planned interim analysis for PFS.

The study will incorporate [REDACTED] OS analyses ([REDACTED] interim analyses and [REDACTED] final analysis). The [REDACTED] OS interim analysis will be performed at the time of the primary PFS analysis, at which time a number of [REDACTED] deaths are projected to have occurred.

[REDACTED] Refer to Section 4.10 for the assumptions and characteristics of the interim and final analysis for OS.

3. STUDY CONDUCT

3.1 RANDOMIZATION ISSUES

Randomized to the two treatment arms will occur in a 1:1 ratio. A permuted-blocked will be applied to ensure a balanced assignment to each treatment arm.

Randomization and stratification will be managed through an IWRS. Randomization will be stratified by the following factors:

- Geographic region (North America vs. Europe vs. Australia, New Zealand, and others)

- Baseline LDH (\leq the ULN vs. $>$ ULN, using central laboratory results)

3.2 INDEPENDENT REVIEW FACILITY

An independent review committee (IRC) will be used for this study. PFS based on the IRC assessments is the secondary endpoint. Specific details, including responsibilities and structure of the IRC are specified in the IRC Charter.

3.3 DATA MONITORING

An iDMC will be employed to conduct periodic evaluations of safety data. All analyses for the iDMC's review will be prepared by an independent data coordinating center (iDCC). Specific details, including responsibilities and structure of the iDMC, are specified in the iDMC Charter.

4. STATISTICAL METHODS

The analyses described in this SAP will supersede those specified in protocol for Study CO39262 for the purpose of a regulatory filing.

4.1 ANALYSIS POPULATIONS

4.1.1 Randomized Population

The randomized population or intent-to-treat (ITT) population is defined as all randomized patients, whether or not study treatment was received. The ITT population will be analyzed according to the treatment assigned at randomization.

4.1.2 Safety Population

The safety population will include all patients who received any amount of any study drug (e.g., atezolizumab, cobimetinib, or vemurafenib), with patients grouped as follows:

- Atezolizumab+cobimetinib+vemurafenib arm: patients who received any amount of atezolizumab with or without any amount of cobimetinib or vemurafenib
- Placebo+cobimetinib+vemurafenib arm: patients who received any amount of cobimetinib or vemurafenib without any amount of atezolizumab

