6.2 SUMMARIES OF CONDUCT OF STUDY

Enrollment, eligibility violations, and patient disposition will be summarized for randomized patients by treatment arm. Study treatment administration will be summarized by treatment arm for all treated patients.

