4.2 ANALYSIS OF STUDY CONDUCT

Study enrollment, major protocol deviations, including major deviations of inclusion/exclusion criteria, and reasons for study discontinuation will be summarized overall and by treatment arm for the ITT population. Study treatment administration and reasons for discontinuation from study treatment will be summarized for the safety population.

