4.5.1 Exposure of Study Medication

Study drug exposure, including treatment duration, number of doses, and dose intensity will be summarized for each treatment arm using descriptive statistics.

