4.5.2 Adverse Events

Verbatim description of AEs will be mapped to Medical Dictionary for Regulatory Activities (MedDRA) thesaurus levels and graded according to NCI CTCAE v4.0. All AEs that occur during or after the first study drug dose will be summarized by treatment arm and NCI CTCAE grade. In addition, serious adverse events (SAEs), AEs (Grade 3–5), [REDACTED] and AEs leading to study drug discontinuation or interruption will be summarized accordingly. AEs leading to dose reduction will be summarized for cobimetinib and vemurafenib.

Multiple occurrences of the same event will be counted once at the maximum severity. The proportion of patients who experience at least one AE will be reported by toxicity term and treatment arm.

All deaths and causes of death will be summarized.

Listings of AEs will include all AEs with an onset that occurred on or after the first study drug treatment up to the data cutoff date.

In addition, deaths, SAEs, [REDACTED], and AEs (Grade 3–5) during the study run-in period, will be summarized. To evaluate safety during triple combination period (i.e., post run-in), SAEs, AEs (Grade 3–5), and AE leading to any study drug discontinuation will be summarized.

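### Grouping safety by receipt of atezolizumab moves Arm B patients who never reach the first infusion into the control group

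*SAP*

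**What the plan says.** SAP 4.1.2 puts in the atezolizumab group everyone who received any atezolizumab. The control group is "patients who received any amount of cobimetinib or vemurafenib without any amount of atezolizumab", whatever arm was assigned. SAP 4.5 repeats the rule for all safety analyses. Sections 1 and 4 of the SAP say that it supersedes the protocol for filing. Protocol 6.5 words its grouping differently, and its example covers only drug given in error.

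The outputs that rest on this population are:

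- Main adverse event tables, SAP 4.5.2: "All AEs that occur during or after the first study drug dose will be summarized by treatment arm".
- Exposure, SAP 4.5.1: "dose intensity will be summarized for each treatment arm".
- Run-in deaths, SAEs and Grade 3–5 events, SAP 4.5.2: these "during the study run-in period, will be summarized", with no statement of a split by arm.
- Triple-combination-period SAEs, Grade 3–5 events and events leading to discontinuation, SAP 4.5.2: neither a split nor a denominator is stated.
- Treatment discontinuation, SAP 4.2: "reasons for discontinuation from study treatment will be summarized for the safety population", again without a stated split.

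In contrast, SAP 4.2 says that "reasons for study discontinuation will be summarized overall and by treatment arm for the ITT population". Protocol 6.2 says "Study treatment administration will be summarized by treatment arm for all treated patients", and Protocol 6.5 puts deaths by arm.

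**The concern.** Receipt of atezolizumab is a post-randomization event that cannot occur in the run-in. Randomization falls within 24 hours before Run-In Day 1 (Protocol Appendix 1), and atezolizumab or its placebo starts only at Cycle 1.

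The protocol itself foresees patients who never get that far:

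- Section 5.1.5.1 requires both oral drugs to be ongoing for entry to Cycle 1.
- The run-in liver rows of Table 3 can end study participation.
- Section 4.6.1 lets a patient with a new contraindication stay on cobimetinib and vemurafenib alone.

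In Arm B all of these patients become control patients. Their Arm A counterparts stay where they are. The rule is therefore asymmetric: control carries the early failures of both arms, and the experimental group consists only of patients who came through the run-in.

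Comparing safety between the arms is a stated objective. At stake are the run-in safety summary, the treatment-discontinuation table and the triple-period tables. Those are the outputs a reader would use to judge early tolerability and the effect of adding atezolizumab.

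**Working it through.** There is no figure in the plan to reproduce, because the point concerns a classification rule. The size has to be illustrated on assumptions.

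**Inputs from the documents.** About 500 patients randomized 1:1 (SAP 2), so n = 250 per arm.

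**Assumptions.** All randomized patients are treated, and true risks are equal in the two arms. A fraction q of each arm is never infused. Of these, a share f continues on oral drugs and the rest stop all drugs or die. Write s = q(1−f) and c = qf. The documents give none of these rates.

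**Group sizes under the SAP rule (expected counts).** Atezolizumab n(1−q), control n(1+q). At q = 2%, 5%, 10% this is 245 v 255, 237.5 v 262.5 and 225 v 275.

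**Run-in discontinuation of all drugs.** The atezolizumab group has 0. Control has 2s/(1+q), because both arms' stoppers sit there. The true rate is s in each arm.

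| f | q = 2% | q = 5% | q = 10% |
|---|---|---|---|
| 0 | 0 v 3.9% | 0 v 9.5% | 0 v 18.2% |
| 25% | 0 v 2.9% | 0 v 7.1% | 0 v 13.6% |
| 50% | 0 v 2.0% | 0 v 4.8% | 0 v 9.1% |

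For example, q = 5% and f = 0 gives 2 × 0.05 / 1.05 = 9.5%, against a true 5% in both arms.

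**Run-in deaths.** At 0.4%, 1% or 2% per arm, control has 2 × 250 × the rate, that is 2, 5 or 10 deaths. The atezolizumab group has 0.

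**Run-in Grade 3–5 events.** Let the rate be w in never-infused patients and r in the others. The control rate is [2qw + (1−q)r]/(1+q) and the atezolizumab rate is r, so the spurious excess in control is 2q(w−r)/(1+q). With w from 50% to 80% and r from 20% to 40%:

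- q = 2%: 0.4 to 2.4 points
- q = 5%: 1.0 to 5.7 points
- q = 10%: 1.8 to 10.9 points

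If w = r, the excess is nil.

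**Triple-period tables on whole safety-group denominators.** Let the rate be p in everyone still treated and 0 in those who stopped. The atezolizumab rate is p and the control rate is p(1−s+c)/(1+s+c). With p = 50%:

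| f | q = 2% | q = 5% | q = 10% |
|---|---|---|---|
| 0 | 50 v 48.0% | 50 v 45.2% | 50 v 40.9% |
| 50% | 50 v 49.0% | 50 v 47.6% | 50 v 45.5% |

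**After regrouping by randomized arm,** with triple-period tables limited to patients who had an infusion of atezolizumab or placebo, the groups are 250 v 250 for the run-in. The rates become s v s for discontinuation and p v p for the triple period, so the artificial difference is zero.

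**The case against.** Several counter-arguments have force.

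- **The split is not stated.** The SAP says by arm for the main adverse event and exposure tables, but not for the run-in, triple-period or treatment-discontinuation outputs. The structural zero is therefore conditional on a grouped display. This stands as a condition. However, SAP 4.5 defines these groups for all safety analyses and calls them arms, and Protocol 6.2 and 6.5 put treatment administration and deaths by arm, so a grouped display is the natural reading.
- **The triple-period denominator is not stated.** If it already covers only patients who entered that period, most of the dilution goes. This also stands; what remains is mainly never-infused Arm B patients still on oral drugs.
- **As-received grouping describes exposure fairly for many of these patients.** Treatment on run-in Days 1–21 is identical in both arms, and Protocol 4.6.1 describes continuing at the control vemurafenib dose. This is true, and it is why the rule can stay for cumulative tables. But where both arms are correctly treated without atezolizumab, receipt cannot separate them. Arm B patients who reach Days 22–28 also bring a different vemurafenib schedule into the control exposure summaries.
- **ITT tables recover part of it.** OS is by assigned arm (except deaths without a complete date, SAP 4.9), and so are study exits, including the run-in liver exits. They do not supply run-in SAEs, Grade 3–5 events or reasons for stopping treatment by assigned arm.
- **The size is assumed.** The largest figures need 10% never infused together with f = 0 or widely separated event rates. An approved starting dosage, performance status 0–1 and the option to reduce doses or extend the run-in all suggest lower attrition. That limits the size, not the mechanism.

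**Conclusion.** The concern holds. The SAP's rule sends never-infused Arm B patients to control, and nothing in either document restores assigned-arm grouping for adverse event or treatment-discontinuation outputs. Wherever these are shown by safety group, the atezolizumab group has essentially no run-in deaths and no run-in stops of all drugs. That is true at any attrition rate.

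How large the distortion is depends on unknown rates. At 2% to 10% never infused, apparent run-in discontinuation would be 0% against 2.0% to 18.2%, depending on how many continue on oral drugs. The triple-period distortion runs in the opposite direction and arises only with whole-group denominators, so no net direction can be claimed for cumulative adverse event incidence. Infused Arm B patients keep their run-in events, and PFS and OS are not touched. This should be fixed, but it does not threaten the primary conclusion.

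**What to change.** Amend SAP 4.2 and 4.5.2 as follows:

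1. Present run-in deaths, SAEs, Grade 3–5 events and treatment discontinuations by randomized arm for all treated patients, and state this in the text. Regroup a patient only when the wrong arm's drug was given.
2. Restrict triple-combination-period tables, in both arms, to patients with at least one infusion of atezolizumab or atezolizumab placebo.
3. Report how many Arm B patients were never infused, and show separately those who continued on cobimetinib and vemurafenib under Protocol 4.6.1.
4. Keep the as-received grouping for the overall cumulative adverse event and exposure tables if wanted, with a version by randomized arm as a sensitivity table.

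The cost is SAP wording, one population flag and a few extra tables; no new data are needed. Experimental-arm run-in figures may look slightly less favourable. The triple-period tables would compare patients selected by reaching infusion, but by the same rule in both arms, and never-infused patients still on oral drugs would be seen only in the separate display under item 3.

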4.1.3 Pharmacokinetic-Evaluable Population

The PK-evaluable population is defined as all patients who have received any dose of study drug and for whom at least one evaluable PK sample is collected.

4.2 ANALYSIS OF STUDY CONDUCT

Study enrollment, major protocol deviations, including major deviations of inclusion/exclusion criteria, and reasons for study discontinuation will be summarized overall and by treatment arm for the ITT population. Study treatment administration and reasons for discontinuation from study treatment will be summarized for the safety population.

4.3 ANALYSIS OF TREATMENT GROUP COMPARABILITY

Demographic characteristics, such as age, race/ethnicity, baseline disease characteristics, and stratification factors will be summarized for the ITT population. Descriptive statistics (mean, median, SD, and range) will be presented for continuous data, and frequencies and percentages will be presented for categorical data.

4.4 EFFICACY ANALYSES

Unless otherwise noted, all efficacy analyses will include the ITT population, and patients will be grouped according to the treatment assigned at randomization. The stratification factors will be those used for randomization and will be obtained from the IWRS (geographic region and baseline LDH). Due to the potential risk of over-stratification ([Akazawa et al., 1997](#)), if at least one stratum (i.e., a combination of stratification factor levels across geographic region and baseline LDH) has fewer than 10 PFS events across treatment arms, the stratification factor (one of two stratification factors: geographic region and baseline LDH per IWRS) which contains the level with the smallest number of patients will be removed from the stratified analyses. The removal of the stratification factors will continue until there is no stratum with fewer than 10 PFS events. The final set of stratification factors used in stratified analyses will be applied to all endpoints where stratified analyses are planned.

4.4.1 Primary Efficacy Endpoint

The primary efficacy analysis will be the comparison of PFS, as determined by the investigator, between the two treatment arms using the stratified log-rank test at an overall 0.05 significance level (two-sided).

The statistical hypothesis of this study is as follows:

- H_0 : PFS (Arm A)=PFS (Arm B)
- H_1 : PFS (Arm A)≠PFS (Arm B)

PFS (Arm A) represents the survival function of PFS in the placebo+cobi+vem arm, and PFS (Arm B) represents the survival function of PFS in the atezo+cobi+vem arm.

PFS, as assessed by the investigator, is defined as the time from randomization to the first occurrence of disease progression, as determined by the investigator according to RECIST v1.1, or death from any cause, whichever occurs first. Data for patients who have not experienced disease progression or death at the time of analysis data cut-off will be censored at the date of last tumor assessment. Data for patients without post-baseline tumor assessment will be censored at randomization date.

The hazard ratio (HR) for PFS will be estimated using a stratified Cox model, and two-sided 95% CIs for the HR will be provided. Results from an unstratified analysis will

also be presented. Kaplan-Meier methodology will be used to estimate the median PFS for each treatment arm, and Kaplan-Meier curves will be produced. The 95% CI of the median PFS for each treatment arm will be constructed using the Brookmeyer and Crowley method ([Brookmeyer and Crowley 1982](#)).

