6.4.1 Primary Efficacy Endpoint

The primary analysis will be a comparison of PFS as determined by the investigator between the two treatment arms using a stratified log-rank test at an overall 0.05 significance level (two sided).

The statistical hypothesis of this study is as follows:

- H_0 : PFS (Arm A)=PFS (Arm B)
- H_1 : PFS (Arm A)≠PFS (Arm B)

PFS (Arm A) represents the survival function of PFS in the placebo+cobi+vem arm, and PFS (Arm B) represents the survival function of PFS in the atezo+cobi+vem arm.

PFS, as assessed by investigator, will be the primary endpoint evaluated. PFS is defined as the time from randomization to the first occurrence of disease progression, as determined by the investigator according to RECIST v1.1, or death from any cause, whichever occurs first. Data for patients who have not experienced disease progression or have died will be censored at the last tumor assessment date. Data for patients with no post-baseline tumor assessment will be censored at randomization.

The HR for PFS will be estimated using a stratified Cox model. Two-sided 95% CIs for the HR will be provided. The stratified analyses will incorporate two stratification factors: geographic region (North America vs. Europe vs. Australia, New Zealand, and others) and baseline LDH (\leq ULN vs. $>$ ULN, using central laboratory result). Results from an unstratified log-rank test and the unstratified HR will also be presented. Kaplan-Meier methodology will be used to estimate median PFS for each treatment arm, and Kaplan-Meier curves will be provided.

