1. BACKGROUND

This Statistical Analysis Plan (SAP) provides details of the planned analyses and statistical methods for Study CO39262 (IMspire150): a Phase III, double-blinded, randomized, placebo-controlled study of atezolizumab plus cobimetinib and vemurafenib versus placebo plus cobimetinib and vemurafenib in previously untreated *BRAF^{V600}* mutation positive patients with unresectable locally advanced or metastatic melanoma. The background for the study can be found in the study protocol.

It is anticipated that positive results from Study CO39262 will support the submission of filing applications globally for the use of atezolizumab plus cobimetinib and vemurafenib for the treatment of the previously untreated *BRAF^{V600}* mutation positive patients with unresectable locally advanced or metastatic melanoma. For registration purposes, the analyses outlined in this SAP will supersede those specified in the protocol.

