4.4.4 Exploratory

4.4.5 Sensitivity Analyses

4.4.5.1 Missing Tumor Assessment

The impact of missed scheduled tumor assessments on PFS will be assessed. If patients missed two or more consecutive assessments scheduled immediately prior to the date of disease progression per RECIST v1.1 or death, a sensitivity analysis will be performed where patients who missed two or more scheduled assessments immediately prior to the date of disease progression per RECIST v1.1 or death will be censored at date of the last tumor assessment prior to the missed visits, or at randomization date if no post-baseline tumor assessment prior to the missed visits.

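### The PFS rule for patients with no post-baseline scan is not limited to event-free patients, so read literally it censors at randomization a death that the PFS definition counts as an event

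*SAP*

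**What the plan says.** SAP 2.2.1 defines the primary endpoint as time to investigator-determined progression "or death from any cause, whichever occurs first". SAP 4.4.1 repeats this, and neither place requires a prior scan for a death to count.

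SAP 4.4.1 then gives two censoring sentences. The first concerns "Data for patients who have not experienced disease progression or death at the time of analysis data cut-off" and censors them at the last tumor assessment. The second reads "Data for patients without post-baseline tumor assessment will be censored at randomization date" and does not repeat the event-free condition.

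Protocol 6.4.1 gives the same pair in different words: "Data for patients who have not experienced disease progression or have died will be censored at the last tumor assessment date" and then "Data for patients with no post-baseline tumor assessment will be censored at randomization". The protocol synopsis has both sentences, and SAP Appendix 1 reprints them.

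SAP 4.4.2.1 applies the methods of 4.4.1 to IRC-assessed PFS. For registration purposes, SAP Section 1 says that "the analyses outlined in this SAP will supersede those specified in the protocol".

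**The concern.** A patient who dies without a post-baseline tumor assessment has had a PFS event by definition, and is also a patient without a post-baseline assessment. The definition gives an event on the date of death; the fallback gives zero follow-up and no event. A programmer working from the sentences as written could implement either.

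The protocol's first sentence makes this worse. Its grammar places patients who have died among those to be censored, so it cannot supply the condition that its second sentence lacks.

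At stake are the number of primary events and, if unscanned deaths differ between arms, the primary hazard ratio. The first scheduled scan is at Week 8 (±1 week) from Run-In Day 1 (Protocol 4.5.5), so the patients concerned are mainly, though not only, those who die early.

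**Working it through.** **1. What the text settles.** The plan gives no figure to reproduce, so the first step is to set the relevant places side by side.

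- SAP 2.2.1 and 4.4.1, event definition: death counts, with no scan requirement. An unscanned death is an event.
- SAP 4.4.1, first censoring sentence: limited to patients with neither progression nor death. An unscanned death falls outside it.
- SAP 4.4.1, second sentence: all patients without a post-baseline assessment. Literally, an unscanned death falls inside it.
- Protocol 6.4.1, synopsis and SAP Appendix 1: the second sentence is equally unqualified, and the first literally includes the dead.
- SAP 4.4.2.4 (OS): also has a randomization-date fallback, but it depends on missing survival information, which a patient with a recorded death does not have. It limits itself; the PFS fallback, which depends on scans, does not.
- SAP 4.4.5.1: a sensitivity analysis that censors progressions or deaths after two or more missed scans at the last earlier assessment, "or at randomization date if no post-baseline tumor assessment prior to the missed visits". For a death with no scan at all, this changes nothing if the primary analysis has already censored it at randomization. It therefore suggests that the primary analysis counts it. The evidence is indirect: the clause still has work to do for progression first seen after two missed scans, and it does not reach a death before Week 8.
- SAP 4.9: a death is left out of the efficacy events only when its date is incomplete. This is the only explicit rule removing deaths.

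The definition, 4.4.5.1 and 4.9 point towards counting these deaths, but no sentence says so.

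**2. How many patients.** With 500 randomized (SAP 2.3) and an assumed share q dying unscanned, the number affected is 500 × q: 5 at 1%, 10 at 2% and 20 at 4%.

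**3. Effect on the hazard ratio.** Event count, medians and target hazard ratio are redacted, so these are assumptions: exponential PFS; control median 11 months (the lower end of the 11 to 14 months that Protocol 1.1 gives for combined BRAF and MEK inhibition); underlying hazard ratio 0.70; other events seen no earlier than Week 8 (56/30.4375 = 1.84 months); 15 months of accrual; cut-off at month 30; 1:1 allocation. Early deaths are uniform between 0.1 and 1.84 months and all unscanned. A Cox model on 400,000 simulated patients was fitted twice: with early deaths as events, and with the same patients censored at day 0.

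| Unscanned deaths, control / experimental | HR, counted | HR, censored at day 0 | Events per 500, counted / censored |
|---|---|---|---|
| 0% / 0% | 0.694 | 0.694 | 343 / 343 |
| 1% / 1% | 0.695 | 0.691 | 344 / 339 |
| 2% / 2% | 0.703 | 0.695 | 346 / 336 |
| 4% / 4% | 0.707 | 0.692 | 349 / 329 |
| 1% / 3% | 0.725 | 0.696 | 347 / 337 |
| 2% / 4% | 0.732 | 0.700 | 348 / 333 |
| 2% / 6% | 0.753 | 0.695 | 350 / 330 |
| 3% / 1% | 0.684 | 0.697 | 346 / 336 |
| 4% / 2% | 0.688 | 0.697 | 347 / 331 |

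Hazard ratios are good to about 0.01, because tied Week 8 times are not handled exactly.

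**4. Effect on power of the lost events alone.** Schoenfeld's formula, power = Φ(|ln HR| × √D / 2 − 1.96), for D of 300 to 400 and hazard ratios of 0.65 to 0.75 (all assumed): losing 5 to 20 events costs from 0.1 points (D = 400, HR 0.65, 5 lost: 99.1% to 99.0%) to 2.9 points (D = 300, HR 0.75, 20 lost: 70.2% to 67.3%). SAP 2.4 ties the primary analysis to an event count, so the practical cost would be delay rather than power.

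**The case against.** The strongest reply is that the SAP, read as a paragraph, already counts these deaths. It defines the event, limits censoring to patients without progression or death, and then supplies a date for those censored patients who have no assessment to be censored at. The protocol's reference to patients who have died is a slip that contradicts the definition just before it; the SAP body has repaired it, and the SAP governs for registration. This is the more natural reading, and it stands as evidence of intent. It does not remove the defect: the fallback contains no words tying it to the preceding sentence, and SAP Appendix 1 still reprints the unrepaired text.

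A reader might infer that the plan removes every death before the Week 8 scan. The documents do not support that. Protocol 4.5.5 allows scans at any time when progression is suspected, so an early death after an unscheduled scan is unaffected, whereas a later death with no scan at all would be affected.

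A reader might also infer a bias in favor of the experimental arm. Nothing in the documents gives early-death rates by arm. Planned treatment is identical on Days 1 to 21, and atezolizumab or its placebo starts only after the 28-day run-in (Protocol Table 2), so half of the 56 days to the first scan precede the added drug. Entry requires ECOG 0 or 1 and a life expectancy of at least 18 weeks (Protocol 4.1.1). Early deaths also stay visible in OS and in the safety summaries (SAP 4.4.2.4 and 4.5.2).

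**Conclusion.** The concern holds as a wording defect in the primary endpoint rule. Read literally, a death with no post-baseline tumor assessment is censored at randomization, against the PFS definition and the apparent intent of SAP 4.4.5.1 and 4.9. It does not show that the planned analysis is biased, because the likely intent is to count these deaths.

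If the literal reading were programmed, the effect would be negligible with balanced unscanned deaths: a hazard ratio shift of about 0.00 to 0.02 at 1% to 4% per arm. With imbalance it could go either way: by about 0.06 towards the experimental arm at 2% control versus 6% experimental, or by about 0.01 against it at 4% versus 2%. All of these sizes rest on assumed early-death rates, event times and hazard ratio, and on every early death being unscanned.

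**What to change.** In SAP 4.4.1, state that only patients who are alive and progression-free at the data cut-off and have no post-baseline tumor assessment are censored at randomization, and that a death without a post-baseline tumor assessment is a PFS event on the date of death. The complete-date requirement of SAP 4.9 stays as it is.

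In Protocol 6.4.1, the protocol synopsis and SAP Appendix 1, change the first censoring sentence so that it covers patients with neither progression nor death, and add the same limit to the second sentence.

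In SAP 4.4.2.1, state that the rule applies equally to IRC-assessed PFS.

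The cost is a few sentences in two documents. It needs no new data and does not change the design or the error control.
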